## Electrocardiograms

If the subject is unable to visit the study site for an ECG after Day 1, the subject may visit an alternative facility to have the ECG performed according to the guidelines in [Section 7.5.4](#). Qualified study site personnel must order, receive, and review results.

## Audiological Evaluation

At visits after Screening which require audiological evaluation, if the subject is unable to visit the study site or designated ancillary center for audiological evaluation, the audiological history (Part 1 in the Audiometry Study Guide Worksheet for Post Day 1 visits) must be collected during the remote visit per [Appendix 6.2](#) (or during the home health visit per [Appendix 6.5](#)). The audiological evaluation must be performed per [Section 7.5.5](#) at the next available opportunity, even if outside of a protocol-specified visit window.

## Appendix 6.4. Investigational Product

If the safety of a trial subject is at risk because they cannot complete required evaluations or adhere to critical mitigation steps, then discontinuing that subject from investigational product must be considered.

Investigational product may be shipped by courier to study subjects if permitted by local regulations and in accordance with storage and transportation requirements for the investigational product. Pfizer does not permit the shipment of investigational product by mail. The tracking record of shipments and the chain of custody of investigational product must be kept in the subject's source documents/medical records.

If a third-party courier engaged by Pfizer or Pfizer's contract research organization (CRO) **is used** for shipping the investigational product, written consent must be documented in the informed consent document prior to shipping investigational product. If a third-party courier engaged by Pfizer or Pfizer's CRO **is not used** for shipping the investigational product, consent must be verbally obtained (or per local guidelines/regulations) and documented in site's source documents prior to shipping investigational product.

Prior to shipping investigational product to a subject, 1) consent must be obtained and documented as described above, 2) all required safety information listed in [Appendix 6.2](#) must have been collected and reviewed by the investigator, 3) the required laboratory tests from the previous visit must have been reviewed by the investigator, and 4) any additional evaluation (if requested based on investigator judgment) must have been performed, with results submitted to and reviewed by the investigator.

Investigational product cannot be shipped to the subject and must be temporarily discontinued if 1) the laboratory tests from the previous visit have not been reviewed by the investigator OR 2) after reviewing the required information (including that from a remote visit), the investigator cannot make an assessment of whether it is safe for the subject to continue investigational product. Refer to [Section 5.5](#) regarding temporary withholding of investigational product.

The study site may deliver the investigational product to subjects using an acceptable delivery method only if this is consistent with local laws and regulations and the site is able to ship the investigational product according to the guidelines provided by the Sponsor in a separate document.

The amount of investigational product to be shipped should correspond to the amount dispensed per the Impala Quick Reference Guide at the specific study visit which is being conducted remotely. Dispensing and/or shipment of additional investigational product to extend the visit window is not permitted.

Subjects should continue taking the current supply of investigational product until the new supply is received (unless temporary withholding of investigational product is required).

Dosing logs should be shipped with the investigational product.

Study sites should follow up with the subject once the investigational product is received by the subject to review when to start using the new blister cards, the dosing instructions, and completion of the dosing logs.

Subjects should be instructed not to re-use or dispose of any blister cards dispensed at a previous visit.

All blister cards and dosing logs must be returned to the study site at the next on-site visit.

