## 1.6. Dose Rationale

This study will evaluate PF-06651600 administered at a loading dose of 200 mg QD for 4 weeks followed by maintenance doses of 30 mg and 50 mg QD for 20 weeks relative to placebo (until the primary endpoint, Week 24). The maintenance doses will then be continued for an additional 24 weeks. Additionally, doses of 10 mg, 30 mg and 50 mg QD will be evaluated relative to placebo for 24 weeks and continued for an additional 24 weeks as a fixed-dose regimen (ie, without loading dose).

The rationale for the selection of the doses and regimens is based on:

Efficacy and safety results for the initial 24 weeks of PF-06651600 treatment from Study B7931005 in subjects with AA.

Dose/Exposure response relationships observed for PF-06651600 relevant biomarkers.

Safety results for PF-06651600 from Study B7981006 in subjects with RA.

Exposure margins of proposed clinical doses relative to nonclinical no observed adverse effect level (NOAEL)/lowest observed adverse effect level (LOAEL) exposures (Table 1).

An analysis of the initial 24 weeks (primary objective) of the ongoing Phase 2a Study B7931005 was performed at Week 24. In that study, PF-06651600 was evaluated at 200 mg QD for 4 weeks followed by 50 mg QD for 20 weeks compared to placebo. Both safety and efficacy data from the analysis suggest that this dosing regimen of PF-06651600 is appropriate for further investigation.

Mechanistically, PF-06651600 inhibits signaling of the common- $\gamma$  chain receptors for IL-15 and IL-21, which have been implicated in the pathogenic pathways of AA. There is also evidence of modulation of IP-10, which is a marker related to IFN $\gamma$ .

The need for a loading-dose regimen is based on the hypothesis that maximal inhibition of the relevant immunomodulatory pathways at initiation of treatment can accelerate clinical response which can be maintained by the subsequent lower maintenance dose. The 200 mg dose chosen as the loading dose is expected to produce a >70% IL-15 and IL-21 in vitro signaling inhibition, with ~40% reduction in IP-10 levels from baseline. The 200 mg dose has demonstrated acceptable safety over 4 weeks in B7931005 in AA patients and 8 weeks in B7981006 in moderate to severe RA patients as described in [Section 1.4](#).

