### 3. STUDY DESIGN

Study B7981015 will investigate PF-06651600 in subjects with moderate to severe AA. This is a Phase 2b/3, randomized, double-blind, placebo-controlled, dose-ranging study. The study will have a maximum duration of approximately 57 weeks. This includes an up to 5-week Screening period, a 48-week treatment period, and a 4-week follow-up period as shown in [Figure 1](#). The treatment period will be comprised of a placebo-controlled period that includes a 4-week loading phase and a 20-week maintenance phase, followed by a 24-week extension phase. The study will enroll a total of approximately 660 subjects. The study will be conducted at approximately 120 sites.

To be eligible to enroll in this study, subjects must have moderate to severe AA with  $\geq 50\%$  hair loss of the scalp (SALT score  $\geq 50$ ) at both Screening and baseline visits, without evidence of terminal hair regrowth within the previous 6 months and with the current episode of hair loss  $\leq 10$  years. The full list of eligibility criteria for the study is included in [Section 4](#).

Screening will occur within 35 days prior to the first dose of study drug to confirm that subjects meet selection criteria for the study. Photographs will be taken at the Screening Visit to verify eligibility (AA with  $\geq 50\%$  hair loss of the scalp). Eligible subjects will be randomized as described below.

A stratified randomization will be used for operational purposes in order to achieve a target global composition for AT/AU and adolescent subjects in the enrolled population. The targets for enrollment are approximately 40% AT/AU and approximately 15% adolescents.

The randomization will be operationalized as follows. In regions enrolling both adolescents and adults, there will be four strata:

- <18 years of age and AT/AU;
- <18 years of age and not AT/AU;
- ≥18 years of age and AT/AU; and
- ≥18 years of age and not AT/AU.

Within each of these strata, subjects will be randomized in a 2:2:2:2:1:1:1 manner to blinded PF-06651600 and matching placebo for a total of 7 treatment sequences.

[figure not shown]
In regions enrolling only adults, there will be two strata:

- ≥18 years of age and AT/AU; and
- ≥18 years of age and not AT/AU.

In these regions, subjects will be randomized using the same ratio as described for regions enrolling both adolescents and adults.

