## 5.4. Investigational Product Supplies

### 5.4.1. Dosage Form(s) and Packaging

Blinded PF-06651600 and its matched placebo will be provided as tablets for oral administration. The designation “PF-06651600-15” may appear on labeling and indicates a salt. It is equivalent to “PF-06651600” with regard to this protocol. The 50 mg and 10 mg tablets and their matching placebos will be supplied in blister cards and labeled according to local regulatory requirements. Subjects will receive blinded labeled supplies throughout the study.

In order to achieve the proper dosage and maintain the blind throughout the study, tablets will be dispensed in a blinded fashion to ensure that all subjects, regardless of the assigned treatment sequence, will take the same number of tablets/day. To accomplish this, all subjects will take 7 tablets/day during the loading period, 4 tablets/day during the maintenance period, 7 tablets/day during the first 4 weeks of the extension period, and 4 tablets/day for the remainder of the extension period. The number and type of tablets taken per day for each treatment sequence is detailed in Table 2.

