**Table 2. Number and Type of Tablets for Each Treatment Sequence**

Treatment Sequence	Loading Period Day 1 to Week 4 (No. of Tablets)	Maintenance Period Weeks 4 to 24 (No. of Tablets)	First 4 Weeks of Extension Period Weeks 24 to 28 (No. of Tablets)	Remainder of Extension Period Weeks 28 to 48 (No. of Tablets)
A	4 of 50 mg active 3 of 10 mg size pbo	1 of 50 mg active 3 of 10 mg size pbo	1 of 50 mg active 3 of 50 mg size pbo 3 of 10 mg size pbo	1 of 50 mg active 3 of 10 mg size pbo
B	4 of 50 mg active 3 of 10 mg size pbo	1 of 50 mg size pbo 3 of 10 mg active	4 of 50 mg size pbo 3 of 10 mg active	1 of 50 mg size pbo 3 of 10 mg active
C	1 of 50 mg active 3 of 50 mg size pbo 3 of 10 mg size pbo	1 of 50 mg active 3 of 10 mg size pbo	1 of 50 mg active 3 of 50 mg size pbo 3 of 10 mg size pbo	1 of 50 mg active 3 of 10 mg size pbo
D	4 of 50 mg size pbo 3 of 10 mg active	1 of 50 mg size pbo 3 of 10 mg active	4 of 50 mg size pbo 3 of 10 mg active	1 of 50 mg size pbo 3 of 10 mg active
E	4 of 50 mg size pbo 1 of 10 mg active 2 of 10 mg size pbo	1 of 50 mg size pbo 1 of 10 mg active 2 of 10 mg size pbo	4 of 50 mg size pbo 1 of 10 mg active 2 of 10 mg size pbo	1 of 50 mg size pbo 1 of 10 mg active 2 of 10 mg size pbo
F	4 of 50 mg size pbo 3 of 10 mg size pbo	1 of 50 mg size pbo 3 of 10 mg size pbo	4 of 50 mg active 3 of 10 mg size pbo	1 of 50 mg active 3 of 10 mg size pbo

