**Table 2. Number and Type of Tablets for Each Treatment Sequence**

Treatment Sequence	Loading Period Day 1 to Week 4 (No. of Tablets)	Maintenance Period Weeks 4 to 24 (No. of Tablets)	First 4 Weeks of Extension Period Weeks 24 to 28 (No. of Tablets)	Remainder of Extension Period Weeks 28 to 48 (No. of Tablets)
G	4 of 50 mg size pbo 3 of 10 mg size pbo	1 of 50 mg size pbo 3 of 10 mg size pbo	1 of 50 mg active 3 of 50 mg size pbo 3 of 10 mg size pbo	1 of 50 mg active 3 of 10 mg size pbo

Abbreviations: No. = Number; Pbo = placebo.

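### Appendix 6.4 keeps subjects on the current supply until the next one arrives, with no exception for Weeks 4 and 28, so a late delivery can carry 200 mg past its stated 4 weeks

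*Protocol*

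**What the plan says.** Appendix 6.4 (Investigational Product) applies during public emergencies, including the pandemic. It tells subjects: "Subjects should continue taking the current supply of investigational product until the new supply is received (unless temporary withholding of investigational product is required". The only exception is temporary withholding. The same appendix limits supply: "Dispensing and/or shipment of additional investigational product to extend the visit window is not permitted".

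The regimen is stated in three places:

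- Section 1.6 describes the drug as "administered at a loading dose of 200 mg QD for 4 weeks followed by maintenance doses".
- Section 3 describes "a placebo-controlled period that includes a 4-week loading phase and a 20-week maintenance phase, followed by a 24-week extension phase".
- Table 2 gives sequences A and B "4 of 50 mg active 3 of 10 mg size pbo" from Day 1 to Week 4, and gives sequence F the same tablets from Week 24 to Week 28. Sequence G takes "1 of 50 mg active 3 of 50 mg size pbo 3 of 10 mg size pbo" in Weeks 24 to 28, which is 50 mg.

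Tablet counts do not differ by sequence. Section 5.4.1 has all subjects on 7 tablets a day in loading and 4 in maintenance, then "7 tablets/day during the first 4 weeks of the extension period, and 4 tablets/day for the remainder of the extension period".

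**The concern.** At most remote visits the old and new cards carry the same daily dose, so continuing the old ones changes nothing. At Week 4 for A and B, and at Week 28 for F, the old cards hold 200 mg and the new ones 50 mg or 30 mg. A subject who follows Appendix 6.4 while waiting for a courier then departs from the regimen in Section 1.6 and Table 2. The two instructions cannot both be followed.

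Two things are at stake. The first is exposure. The protocol itself separates the doses: Table 1 gives a 9-month dog exposure margin of 1.5 at 200 mg and 6.5 at 50 mg, and Section 1.7 reports platelet and lymphocyte reductions on 200 mg that improved after the switch to 50 mg. The second is treatment fidelity. SAP Section 5.2.2.1 compares loaded with unloaded regimens, and that result decides which exposure-response model is fitted. The exposure summaries in SAP Section 6.6.3 (compliance, doses received, median total dose, days of dosing) would not show directly how long a subject stayed on the 200 mg cards.

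**Working it through.** **Reproducing the stated regimen.** The dose is 4 × 50 mg = 200 mg. From Day 1 to the Week 4 target is 29 − 1 = 28 days. From the Week 24 target to the Week 28 target is 197 − 169 = 28 days. Both agree with 4 weeks.

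**Sequences concerned (Table 2).**

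- Week 4: A goes from 200 to 50 mg and B from 200 to 30 mg. C (50 mg), D (30 mg), E (10 mg), F and G (placebo) do not change.
- Week 28: F goes from 200 to 50 mg. A, C and G (50 mg), B and D (30 mg) and E (10 mg) do not change.

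**Planned numbers.** The ratio 2:2:2:2:1:1:1 sums to 11, and 660 / 11 = 60. A + B = 120 + 120 = 240 (36.4%) at Week 4. F = 60 (9.1%) at Week 28. These are the subjects in the exposed sequences, not the subjects expected to overrun.

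**Length of an overrun.** Overrun in days = max(0, visit offset from target day + transit days), capped by the tablets left. The offset runs from −3 to +3: Table 8 of the protocol gives Days 26 to 32 for Week 4 and Days 194 to 200 for Week 28, the same as the ordinary windows. Transit time is not in the documents, so 0, 1, 3 and 7 days are assumed.

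| Remote visit on Day | 0 days | 1 day | 3 days | 7 days |
|---|---|---|---|---|
| 26 or 194 | 0 | 0 | 0 | 4 |
| 29 or 197 | 0 | 1 | 3 | 7 |
| 32 or 200 | 3 | 4 | 6 | 10 |

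The largest value, 10, is 3 days from the visit window plus 7 from transit. The 3 days arise equally at an on-site visit on Day 32.

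The Week 28 figures count from Day 197 and take the extension to have started on Day 169. Week 24 has its own ±7-day window, so F's total time on these cards shifts with it, whether or not Appendix 6.4 is in use.

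**Whether existing controls settle the changeover.**

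- The bar on extra product (Appendix 6.4) and dispensing to the visit schedule (Section 5.4.2) cap the overrun but do not prevent it. The spare days per card are not stated.
- Appendix 6.4 stops dosing if previous-visit laboratory results are unreviewed or safety cannot be assessed. Appendix 6.3 withholds product if samples miss the extended window, which closes on Day 36 for Week 4 and Day 218 for Week 28. Neither trigger is a change of dose.
- The site contact about starting new cards comes once they have been received, after any overrun.

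**The case against.** The strongest reply is that an overrun needs three things together: a remote Week 4 or Week 28 visit, delivery after the target day, and tablets left over. A visit on Day 26 with up to 3 days' transit gives none. The 4 weeks are not fixed to the day either, since both visits carry ±3 days. Section 1.6 also cites acceptable safety of 200 mg over 8 weeks in rheumatoid arthritis. All of this stands and limits the size of the point. It does not remove the conflict between the two instructions.

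Several stronger readings are tempting, and the documents do not support them:

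- **That the rule always prolongs 200 mg, or affects 300 subjects.** The figure 240 + 60 = 300 counts the exposed sequences. How many would have a remote changeover visit and a late delivery is unknown.
- **That the overrun is 9 days, or 32%.** This can be built by assuming that each Week 2 supply covers Day 12 to Day 32 (20 doses), starting it on Day 18 and running it to Day 37: (37 − 28) / 28 = 32%. The overage is assumed, 3 of the 9 days belong to the ordinary window, and the new cards would have to be still missing 5 days after the latest permitted Week 4 visit.
- **That the site could not notice.** Sites cannot see the dose, but they can see that a subject is still on 7-tablet cards. Dosing logs are reviewed at telehealth visits (Appendix 6.2) and cards are returned.
- **That the loading comparison is compromised.** SAP Section 5.2.2.1 uses a yes/no loading indicator for Week 24 response in the 30 mg and 50 mg arms. Extra days do not change that indicator for A or B, and sequence F's 200 mg period falls after Week 24. No material bias is shown.
- **That barring extra supply contradicts using what is left.** One rule governs supply and the other governs drug already dispensed.

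**Conclusion.** The point holds as a conflict between a stated rule and the stated regimen at two changeovers: Week 4 for A and B (about 240 planned) and Week 28 for F (about 60 planned). An overrun occurs only if delivery is late and tablets remain. It is 0 to 10 days past the target day for an assumed transit of 0 to 7 days, up to 3 of those days come from the ordinary visit window, and the tablets left set the cap. The overage, the transit times and the number of subjects affected are not in the documents, so no expected exposure can be calculated. No sample size, power or alpha figure depends on this, and only A and B bear on the Week 24 loading comparison. Requirements to report protocol deviations (Appendix 6) and to list COVID-affected subjects (SAP Section 6.7) would help document an overrun, but they do not say what applies at the changeover. The correction is worth making because it is specific and cheap, and because it concerns exposure to the highest dose.

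**What to change.** Reconcile Appendix 6.4 with Sections 1.6 and 3 and Table 2 by stating what applies at the Week 4 and Week 28 visits when the new cards have not arrived. The content is for the sponsor's medical team; no dose or rule is proposed here. Word it by visit, for all sequences. Because every subject goes from 7 to 4 tablets a day at both visits, such wording reveals no allocation.

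Add to the SAP a listing of days on the 7-tablet cards per subject, by sequence, for Day 1 to Week 4 and for Weeks 24 to 28, so that any overrun can be seen.

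The cost is one sentence in Appendix 6.4, a site letter and one listing.

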### **Appendix 6.5. Home Health Visits**

A home health care service may be utilized to facilitate scheduled visits per the [Schedule of Activities](#) if operationally feasible and will be conducted according to local regulations. Home health visits include a healthcare provider conducting an in-person study visit at the subject's location, rather than an in-person study visit at the site.

If a third-party engaged by Pfizer or Pfizer's CRO is used for home health visits, written consent must be documented in the informed consent document prior to conducting the first home health visit. If a third-party engaged by Pfizer or Pfizer's CRO is not used for home health visits, consent must be verbally obtained and documented in site's source documents (or per local guidelines/regulations) prior to conducting the first home health visit.

The following may be performed during a home health visit:

- Review dosing logs and record investigational product, including doses taken and any interruptions in intake of investigational product (ie, missed doses) since the last contact, and calculate compliance.

- Review and record any AEs and SAEs since the last contact. Refer to [Section 8](#).

- Review and record any new concomitant medications or changes in concomitant medications since the last contact.

For WOCBP: Review and record contraceptive method and results of pregnancy testing. Confirm that the subject is adhering to the contraception method(s) required in the protocol [Section 4.3.1](#). Refer to [Section 7.2](#) of the protocol and [Appendix 6.3](#) regarding pregnancy tests.

For premenarchal female subjects: Check for initiation of menarche.

Collection of updated audiological history (Part 1 in the Audiometry Study Guide Worksheet for Post Day 1 visits) at visits requiring audiological evaluation.

Body temperature and collection method (eg, oral, tympanic, axillary), pulse rate, and respiratory rate (measured by study subject/caregiver).

ECG per [Section 7.5.4](#).

Hematology.

Serum chemistry.

Fasting lipid panel.

Urinalysis.

Pregnancy testing (for WOCBP).

Physical examination.

## **Appendix 6.6. Adverse Events and Serious Adverse Events**

If a subject has a confirmed or suspected COVID-19 infection during the study, this should be reported as an adverse event (AE) or serious adverse events (SAE) and appropriate medical intervention provided. For non-serious COVID-19 infections, temporary discontinuation of the investigational product may be medically appropriate until the subject has recovered from the COVID-19 infection. If this is a serious infection (ie, requires parenteral antimicrobial therapy or hospitalization for treatment or meeting other criteria that require the infection to be classified as a serious adverse event), the subject must be permanently discontinued from investigational product per [Appendix 3.2](#) of the protocol.

## **Appendix 6.7. Efficacy Assessments**

Efficacy assessments listed in [Section 7.6](#) and [Section 7.8](#) are only to be collected during on-site visits. This includes SALT, ELA, EBA, fingernail assessment, CGI-AA, and all patient reported outcomes.

1. VERSION HISTORY

Table 1. Summary of Major Changes in SAP Amendments

Version/Date	Associated Protocol Amendment	Rationale	Specific Changes
1 1 NOV 2018	Original 17 SEP 2018	Not Applicable	Not Applicable
2 11 Aug 2020	Amendment 3 14 July 2020	
 To be consistent with the protocol amendments 1-3. To provide additional details and clarification. 	
 Changed primary endpoint from SALT ≤ 10 at Week 24 to SALT ≤ 20 at Week 24. It was also noted that SALT ≤ 10 will be analyzed as the primary endpoint in a separate analysis where required (Sections 2.1, 2.2, 3.1, 5.1, 6.1). Added PGI-C response at Week 24 will be analyzed as a key secondary endpoint where required (Section 2.1, 2.2, 3.2, 5.1, 6.2). Updated endpoints according to the protocol and provided additional details (Sections 2.1, 3, 6). Added stratified randomization (Section 2.2). Updated power estimation (Section 2.2). Added the study may be unblinded for internal decision-making purposes (Sections 2.2, 7). Added Per protocol analysis set (Section 4.2). Added testing procedure for multiple comparisons for SALT ≤ 10 at Week 24 and SALT ≤ 20 at earlier timepoints if SALT ≤ 20 at Week 24 is the primary endpoint. It was also noted that for regions that request a primary endpoint of SALT ≤ 10 at week 24, a similar approach will be used to control the Type I error for SALT ≤ 20 at Week 24 and SALT ≤ 10 at earlier time points (Section 5.1). Added testing procedure for multiple comparisons incorporating a key secondary endpoint for regions that request PGI-C response at week 24 as a key secondary endpoint where required (Section 5.1.1).

			
 • Added details on data summary in the extension phase (Sections 5.2, 6). • Updated visit windows (Appendix 1). • Added Appendices 4-6.
Version 3 13 November 2020	Protocol Amendment 4 20 October 2020	
 • To comply with the VHP feedback that EU specific endpoints and analysis should be explicitly stated (beyond the verbatim that already existed to manage region specific preferences) in a consistent manner and to align with the protocol Amendment 4 which was updated given this VHP feedback 	
 • It has been specifically clarified that for the European Union (EU) (including the Voluntary Harmonisation Procedure [VHP] countries), the primary objective and primary endpoint will utilize an absolute Severity of Alopecia Tool (SALT) Score of ≤ 10 and not ≤ 20 at Week 24. • Sections 2.1 (study objectives), 2.2 (sample size), 3.1 (primary endpoint), 3.2 (secondary endpoints), 6.1 (analysis of primary endpoint), and 6.2 (analysis of secondary endpoints). • It has been specifically clarified that for the EU (including VHP countries), the evaluation of the effect of PF-06651600 on patient centered outcomes (as measured by Patient’s Global Impression of Change [PGI-C] response at Week 24) is a key secondary objective. The PGI-C response at Week 24 will be analyzed as a key secondary endpoint utilizing an appropriate testing procedure to control overall Type I error. • Sections 2.1 (study objectives), 2.2 (sample size), 3.2 (secondary endpoints), 5.1 (hypotheses and decision rules), 5.1.1 (testing procedure for multiple comparisons incorporating a key secondary endpoint) and 6.2.8 (analysis of PGI-C response). • Objectives and Endpoints table (including footnotes) was updated to clarify which secondary endpoints will be controlled for Type I error based on which SALT parameter at Week 24 (ie, ≤ 20 or ≤ 10) is utilized as the primary endpoint. • Section 2.1 (study objectives). • Endpoints tables was updated to clarify that for the EU (including

			
VHP countries), the endpoints utilizing the HADS will be analyzed as secondary endpoints.
 
 • Sections 2.1 (study objectives), and 3.3.1 (exploratory endpoints). • Added text to clarify that more stringent alpha levels have been advised for regulatory submission of B7981015 in the EU and for the FDA. • Sections 2.2 (sample size) and 5.1 (hypothesis and decision rules).
		
 • General changes, typographical corrections, and clarifications 	
 • Changed the utility weights for the derivation of EQ-5D scores (Section 3.3.1). US utility weights will be used for all participants so that all patients are on the same weighted scale for modeling purposes • Added clarification of the definition of baseline for ECG assessments (Sections 3.4 and 3.5.5). • Correction of grammatical and typographical errors in Sections 2.1, 2.2, 3.3.1, 5.2.1, 5.2.2, 5.3.1, 6.3.8, 6.3.9, 6.3.14, 6.5, 6.6.1, 6.7, 6.7.1, and Appendix 1. • Replaced all text from Sections 5.2.1, 6.1 and 6.2 that mentioned approach for missing data of binary endpoints by a general sentence that refers to Section 5.3.1 • Added Section 6.1.2 to describe the analysis of the primary endpoint in the per protocol analysis set (PPAS). • A standard sentence was used to describe the approach for missing data throughout Section 6.2 to refer back to the missing data approach described in Section 5.3. • HADS cut off values were added to sections 6.3.10 and 6.3.11 for consistency with Section 3.3.1. • Added subset of subjects who received prior pharmacological treatment to AA to Section 6.5 and deleted “requiring discontinuation at any time” in Section 6.7.4.


Version 4 23 April 2021
	
Protocol Amendment 5 13 April 2021
	
 • To align with protocol Amendment 5, specifically to define the endpoints and alpha levels and hypothesis testing for the overall study and to clarify the endpoints and alpha and hypothesis testing for FDA/PMDA and for EMPA and competent authorities in VHP countries and to incorporate changes to the analysis and approach for handling missing due to COVID-19 after feedback received from regulatory agencies. • The FAS was revised based on regulatory feedback to include all subjects who were randomized regardless of whether they received treatment • To provide further details on the definition of the per protocol population based on regulatory feedback • Also, further details of the E_{max} models for the exposure response, and tipping point analysis were provided • Planned COVID-19 related summaries and listings were added • Unblinding of data for PK/PD modelling was added • Several places in this document were corrected for typographical errors. 	
 • Early unblinding for PK/PD modelling was added to Section 2.2 • Further clarification was added to the sample size section 2.2.1 to account for the alphas for the different regions. • Tables 3 and 4 were added to Section 3 to define the endpoints and alpha for the overall study, and clarify the endpoints and alpha for FDA/PMDA and for EMPA and competent authorities in VHP • FAS and PPAS were updated in Sections 4.1 and 4.2 • Hypothesis testing for the overall study was added to Section 5.1 and was further clarified for FDA/PMDA and for and for EMPA and competent authorities in VHP • Tables 5 was added to Section 5.2.1 to clarify the primary and supportive analyses specifically to address handling of missing data due to COVID-19 for the overall study and for FDA/PMDA and for EMPA and competent authorities in VHP • Section 5.2.1 was reorganized into subsections 5.2.1.1, 5.2.1.2, 5.2.1.3 and 5.2.1.4 after the introduction of the primary analysis for the EMA and competent authorities in VHP countries, following advice from regulatory agency • Section 5.2.2. was expanded to provide further details of the E_{max} models for the analysis for exposure response. • Section 5.3.1 was expanded to clarify handling of missing data due to COVID-19 • Section 6.1 was modified to summarize all analyses that are planned for each primary, key secondary and α-controlled endpoints. • Section 6.2 additional detail was provided to clarify handling of
------------------------------------	---	---	--

			
missing data due to COVID-19 for secondary endpoints
 
 • COVID-19 related planned summaries and listings were added to Section 6.7 • In Section 6.7.1, clarification on analyses of AEs of special interest was provided, and the planned summaries of COVID-19 related AEs, and AE summaries by COVID-19 anchor date were added • Analysis of Columbia Suicide Severity Rating Scale analysis was removed from Section 6.7.7 since this scale was only intended for monitoring • Further detail was provided for the interim analysis in Section 7, with regards to the dissemination of results, and to clarify that the interim will have no impact on B7981015 study conduct, analysis, or reporting • Tipping point and E_{max} references were added • Section 9.6 was added to provide further details and specifications of the tipping point analysis. • Section 9.7 was added to provide further specifications for the definition of subgroups for analysis
--	--	--	---

